## 7. PLANNED ANALYSIS

Safety analysis (refer to [Section 7.8](#)) will be performed by and will be presented in Sections 15.1 to 15.4 of the CTR and in Appendix 16.2 and 16.1.13.1.

Inferential statistical analyses of PK endpoints (refer to [Section 7.4](#) and [Section 7.5.2](#)) will also be performed by and will be presented in Section 15.5 of the CTR and in Appendix 16.1.13.3.

Descriptive data analysis of PK endpoints and concentrations will be performed by the department Translational Medicine and Clinical Pharmacology (TMCP) at BI and will be presented in Section 15.6 of the CTR.

The format of the listings and tables will follow the BI standards (see BI-KMED-BDS-HTG-0045 ([6](#))) with the exception of those generated for PK-calculations ([7](#)).

The individual values of all subjects will be listed, sorted by sequence group, subject number, visit and actual treatment (if appropriate).

The listings will be included in Appendix 16.2 of the CTR.

For end-of-text tables, the set of summary statistics for non-PK parameters is:

N	number non-missing observations
Mean	arithmetic mean
SD	standard deviation
Min	minimum
Median	median
Max	maximum

For analyte concentrations, the following descriptive statistics will additionally be calculated:

CV	arithmetic coefficient of variation
gMean	geometric mean
gCV	geometric coefficient of variation

For PK parameters, the following descriptive statistics will additionally be calculated:

CV	arithmetic coefficient of variation
gMean	geometric mean
gCV	geometric coefficient of variation
P10	10th percentile
Q1	1st quartile
Q3	3rd quartile
P90	90th percentile

The data format for descriptive statistics of concentrations will be identical to the data format of the respective concentrations. The descriptive statistics of PK parameters will be calculated using the individual values with the number of decimal places as provided by the evaluation program. Then the individual values as well as the descriptive statistics will be reported with three significant digits in the CTR.

Tabulations of frequencies for categorical data will include all possible categories and will display the number of observations in a category, as well as the percentage (%). Percentages will be rounded to one decimal place and will be based on all subjects in the respective subject set whether they have non-missing values or not. The category 'missing' will be displayed only if there are actually missing values.

Units of variables should be given in the titles or column/row descriptors in square brackets (e.g. [mg]).

#### Exclusion of PK parameters

The ADS ADPP (PK parameters) contains column variables indicating inclusion/exclusion (APEXC) of a PK parameter and an analysis flag comment (APEXCO). All analyses based on the PKS will include parameters if they are not flagged for exclusion, that is APEXCO is equal to "Included".

#### Exclusion of PK concentrations

The ADS ADPC (PK concentrations per time-point or per time-interval) contains column variables ACEXC and ACEXCO indicating inclusion/exclusion (ACEXC) of a concentration and an analysis flag comment (ACEXCO). Exclusion of a concentration depends on the analysis flag comment ACEXCO. For example, if ACEXCO is set to 'ALL CALC', the value will be excluded for all types of analyses based on concentrations. If ACEXCO is set to 'DESC STATS' the value will be excluded from descriptive evaluations per planned time point/time interval. If ACEXCO contains the addition 'TIME VIOLATION' or 'TIME DEVIATION' the value can be used for further analyses based on actual times. If ACEXCO is set to 'HALF LIFE', the value will be excluded from half-life calculation (and, as a consequence, any calculation that relies on  $\lambda_z$ ) only; the value is included for all other analyses.

Further details are given in 001-MCS-36-472\_RD-01 "Noncompartmental Pharmacokinetic / Pharmacodynamic Analyses of Clinical Studies" ([5](#)) and 001-MCS-36-472\_RD-03 "Description of Analytical Transfer Files and PK/PD Data Files" ([11](#)).

## 7.1 DEMOGRAPHIC AND OTHER BASELINE CHARACTERISTICS

Only descriptive statistics are planned for this section of the report, based on the TS.

The data will be summarised in total.

## **7.2 CONCOMITANT DISEASES AND MEDICATION**

Frequency tables are planned for this section of the report, based on the TS.

Concomitant diseases will be coded using the coding system of the Medical Dictionary for Drug Regulatory Activities (MedDRA). Medications will be coded using the World Health Organization Drug Dictionary (WHO-DD). The coding version number will be displayed as a footnote in the respective output.

The diagnoses and medications will be listed. Subjects without any concomitant diagnoses or concomitant therapies should be marked with a “No” in the respective column.

The relevance of the concomitant therapies to the evaluation of PK will be decided no later than at the RPM.

## **7.3 TREATMENT COMPLIANCE**

**Section 4.3 of the CTP:** *Compliance will be assured by administration of all trial medication in the study centre under supervision of the investigating physician or a designee. The measured plasma concentrations of trial medication will provide additional confirmation of compliance.*

It is not intended to list the compliance separately. Any deviations from complete intake will be addressed in the RPM (cf. TSAP [Section 6.2](#)) and described in the CTR.

## **7.4 PRIMARY ENDPOINTS**

Relative bioavailability of BI 894416 in plasma is to be determined on the basis of the primary and secondary pharmacokinetic endpoints  $AUC_{0-\infty}$ ,  $C_{max}$  and  $AUC_{0-tz}$  (see [Section 5.1](#) and [Section 5.2](#)).

### **7.4.1 Primary analysis of the primary endpoints**

**Section 7.3.1 of the CTP:** *The statistical model used for the analysis of the primary endpoints will be a mixed effects model on the logarithmic scale. That is, the PK endpoints will be log-transformed (natural logarithm) prior to fitting the mixed effects model. This model will include effects accounting for the following sources of variation: subject and treatment. The effect ‘subjects’ will be considered as random, whereas treatment will be considered as fixed. The model is described by the following equation:*

$y_{km} = \mu + s_m + \tau_k + e_{km}$ , where

$y_{km}$  = logarithm of response measured on subject  $m$  receiving treatment  $k$ ,

$\mu$  = the overall mean,

$s_m$  = the effect associated with the  $m^{\text{th}}$  subject,  $m = 1, 2, \dots, n$

$\tau_k$  = the  $k^{\text{th}}$  treatment effect,  $k = 1, 2,$

$e_{km}$  = the random error associated with the  $m^{\text{th}}$  subject who received treatment  $k$ .

where  $s_m \sim N(0, \sigma_B^2)$  i.i.d.,  $e_{km} \sim N(0, \sigma_W^2)$  i.i.d. and  $s_m, e_{km}$  are independent random variables. The indices 'B' and 'W' correspond to 'between' and 'within' variability, respectively.

Point estimates for the ratios of the geometric means (test/reference) for the primary endpoints (see [Section 5.1](#)) and their two-sided 90% confidence intervals (CIs) will be provided.

For each endpoint, the difference between the expected means for  $\log(T)$ - $\log(R)$  will be estimated by the difference in the corresponding adjusted means (Least Squares Means). Additionally their two-sided 90% confidence intervals will be calculated based on the residual error from the mixed effects model and quantiles from the  $t$ -distribution. These quantities will then be back-transformed to the original scale to provide the point estimate and 90% CIs for each endpoint.

The implementation for this analysis will be accomplished by using the XPKISTAT macro, based on PKS, and option BWU (Bioavailability/Bioequivalence, within-subject design, and uncontrolled with respect to time).

## **7.5        SECONDARY ENDPOINTS**

### **7.5.1      Key secondary endpoints**

This section is not applicable as no key secondary endpoint has been specified in the protocol.

### **7.5.2      Secondary endpoints**

The secondary PK parameter  $AUC_{0-tz}$  will be assessed using the same methods as described for the primary endpoints.

## **7.6.2      Safety endpoints**

Refer to TSAP [Section 7.8](#) for a description of the analysis of safety and tolerability of BI 894416.

## **7.7        EXTENT OF EXPOSURE**

Descriptive statistics are planned for this section of the report based on the TS. The date and time of drug administration will be listed for each subject.

## **7.8 SAFETY ANALYSIS**

All safety analyses will be performed on the TS.

The safety data for treated subjects who failed to complete the study (dropouts or withdrawals) will be reported as far as their data are available. All withdrawals will be documented and the reason for withdrawal recorded.

### **7.8.1 Adverse Events**

AEs will be coded with the most recent version of MedDRA.

The analyses of AEs will be descriptive in nature and will be based on BI standards as presented in “Analysis and Presentation of Adverse Event Data from Clinical Trials – Display Template” [BI-KMED-BDS-HTG-0041] (8). All analyses of AEs will be based on the number of subjects with AEs and not on the number of AEs.

For analysis multiple AE occurrence data on the eCRF will be collapsed into one AE provided that all of the following applies:

- All AE attributes are identical (lower level term (LLT), intensity, action taken, therapy required, seriousness, reason for seriousness, relationship, outcome, AE of special interest (AESI))
- The occurrences were time-overlapping or time-adjacent (time-adjacency of two occurrences is given if the second occurrence started within one hour after end of the first occurrence).

The analysis of AEs will be based on the concept of treatment emergent AEs. That means that all AEs will be assigned to screening or on-treatment phases as defined in [Section 6.1](#). AEs will be analysed based on actual treatments, as defined in [Table 6.1: 1](#)

**Section 5.2.6.1.4 of the CTP:** *The following are considered as AESIs:*

- **Hepatic injury**  
*A hepatic injury is defined by the following alterations of hepatic laboratory parameters:*
  - *An elevation of AST (aspartate transaminase) and/or ALT (alanine transaminase)  $\geq 3$ -fold ULN combined with an elevation of total bilirubin  $\geq 2$ -fold ULN measured in the same blood sample, or*
  - *Aminotransferase (ALT, and/or AST) elevations  $\geq 10$  fold ULN*

*These lab findings constitute a hepatic injury alert and the subjects showing these lab abnormalities need to be followed up according to the 'DILI checklist' provided in the ISF or in eDC, as applicable. In case of clinical symptoms of hepatic injury (icterus, unexplained encephalopathy, unexplained coagulopathy, right upper quadrant*

*abdominal pain, etc.) without lab results (ALT, AST, total bilirubin) available, the Investigator should make sure that these parameters are analysed, if necessary in an unscheduled blood test. Should the results meet the criteria of hepatic injury alert, the procedures described in the DILI checklist should be followed.*

According to ICH E3 ([9](#)), AEs classified as ‘other significant’ need to be reported and will include those non-serious and non-significant AE with

- (i) ‘action taken = discontinuation’ or ‘action taken = reduced’, or
- (ii) marked haematological and other lab abnormalities or lead to significant concomitant therapy as identified by the Clinical Monitor/Investigator at a RPM.

An overall summary of AEs (including AESIs and other significant AEs) will be presented.

The frequency of subjects with AEs will be summarised by treatment, primary system organ class (SOC) and preferred term (PT). Separate tables will be provided for subjects with other significant AEs according to ICH E3 ([9](#)), for subjects with serious AEs, for subjects with drug-related AEs, for subjects with drug related serious adverse events and for subjects with AESIs. In addition, the frequency of subjects with AEs will be summarised by treatment, worst intensity, primary system organ class (SOC) and preferred term (PT).

The SOCs and PTs will be sorted by frequency (within SOC). The MedDRA version number will be displayed as a footnote in the respective output.

In addition, frequencies of subjects with non-serious AEs that had an incidence of > 5% for at least one treatment will be summarised by treatment, primary SOC and PT.

For disclosure of adverse events on EudraCT, additional information not included in a standard AE analysis will be performed. The following three entries will be created:

- Adverse Events per arm for disclosure on EudraCT
- Non-serious Adverse Events for disclosure on EudraCT
- Serious Adverse Events for disclosure on EudraCT

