### 7.3.4 Safety analyses

Safety will be analysed based on the assessments described in Section [2.2.2.2](#). All treated subjects (TS, refer to Section [7.2](#)) will be included in the safety analysis. Safety analyses will be descriptive in nature and based on BI standards. No hypothesis testing is planned.

For all analyses, the treatment actually administered (= treatment at onset) to the subject will be used (any deviations from the randomised treatment will be discussed in the minutes of the Report Planning Meeting).

Treatments will be compared in a descriptive way. Tabulations of frequencies/proportions will be used to evaluate categorical (qualitative) data, and tabulations of descriptive statistics will be used to analyse continuous (quantitative) data.

Measurements (such as ECG, vital signs, or laboratory parameters) or AEs will be assigned to treatments (see Section [4.1](#)) based on the actual treatment at the planned time of the measurement or on the recorded time of AE onset (concept of treatment emergent AEs). Therefore, measurements planned or AEs recorded prior to first intake of trial medication in period 1 will be assigned to the screening period, those between treatment with BI 894416 in period 1 and first treatment with rifampicin in period 2 are attributed to the treatment interval “BI 894416 alone”, those between first treatment with rifampicin in period 2 and treatment with BI 894416 in period 2 are attributed to the treatment interval “rifampicin alone” and those occurring between treatment with BI 894416 in period 2 and the individual subject’s end of trial are attributed to the treatment interval “BI 894416 + rifampicin”. These assignments including the corresponding time intervals will be defined in detail in the TSAP. Note that AEs occurring after the last per protocol contact but entered before final database lock will be reported to Pharmacovigilance only and will not be captured in the trial database.

Additionally, further treatment intervals (analysing treatments) may be defined in the TSAP in order to provide summary statistics for time intervals, such as combined treatments, on-treatment totals, or periods without treatment effects (such as screening and follow-up intervals).

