## **6. GENERAL ANALYSIS DEFINITIONS**

### **6.1 TREATMENTS**

For basic study information on investigational products, assignment of treatment sequences and selection of doses, please see CTP, Sections 3 and 4.

The study will be performed as an open-label trial with two treatments (T and R) and one fixed sequence (R then T).

In total, it was planned to assign 16 healthy male subjects.

For details of dosage and formulation see Table 6.1: 1 below:

Table 6.1: 1 Treatments and labels used in the analysis

Treatment	Short label
R BI 894416, 2*25 mg tablet, po, qd	BI
T BI 894416, 2*25 mg tablet, qd + rifampicin, 600 mg tablet, qd	BI+Rifa

**Section 1.2.3 of the CTP:** *The Residual Effect Period (REP, i.e., the period after the last dose with measurable drug levels and/or pharmacodynamic effects still likely to be present) of BI 894416 has not been defined yet. [...] For the use of rifampicin in this trial, the REP is defined as 6 days.*

The following separate study phases will be defined for the analyses of AEs:

Table 6.1: 2 Flow chart of analysis phases for statistical analyses of AEs

Study analysis phase	Label	Start (inclusive)	End (exclusive)
Screening	Screening	Date of informed consent	Date/time of administration of BI 894416 in treatment period 1
On-treatment	BI	Date/time of administration of BI 894416 in treatment period 1	Date/time of first administration of rifampicin in treatment period 2
On-treatment	Rifa	Date/time of first administration of rifampicin in treatment period 2	Date/time of administration of BI 894416 in treatment period 2
On-treatment	BI+Rifa	Date/time of administration of BI 894416 in treatment period 2	0:00h on the day after EoT visit

**Section 7.3.4 of the CTP:** *Note that AEs occurring after the last per protocol contact but entered before final database lock will be reported to Pharmacovigilance only and will not be captured in the trial database.*

Please note that all AEs reported between start of trial drug administration and the last per-protocol contact will be considered on treatment.

The following AE displays will be provided in the report:

Section 15.3 and Appendix 16.1.13.1.8 (for ClinicalTrials.gov and EudraCT only) of the CTR displays:

In these displays, the on-treatment phase will be analysed (labelled with the name of the study treatment (short label)). Screening period will not be included in this analysis.

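### The SAP's rule for collapsing adverse event occurrences does not stop at an analysis-phase boundary, so a matching post-dose occurrence can be counted in the phase before the dose

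*SAP*

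**What the plan says.** SAP 7.8.1 introduces the rule as follows: "For analysis multiple AE occurrence data on the eCRF will be collapsed into one AE provided that all of the following applies". Two conditions follow. The first is "All AE attributes are identical (lower level term (LLT), intensity, action taken, therapy required, seriousness, reason for seriousness, relationship, outcome", together with the special-interest flag. The second is that the occurrences overlap or are adjacent, where "time-adjacency of two occurrences is given if the second occurrence started within one hour after end of the first occurrence". Treatment, analysis phase and an intervening dose appear in neither condition.

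The same section then says that "all AEs will be assigned to screening or on-treatment phases as defined in" SAP 6.1. Table 6.1: 2 there places the phase boundaries at dosing times:

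- Screening gives way to BI at "Date/time of administration of BI 894416 in treatment period 1".
- BI gives way to Rifa at the first rifampicin dose.
- Rifa gives way to BI+Rifa at "Date/time of administration of BI 894416 in treatment period 2".

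Protocol 7.3.4 assigns AEs to treatments based "on the recorded time of AE onset (concept of treatment emergent AEs").

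SAP 6.1 leaves Screening out of the Section 15.3 and registry-disclosure displays but includes it in Section 15.4 and the Appendix 16.2 listings. It adds a total over the phases involving BI 894416 and a total over all on-treatment phases. It also states that "all AEs reported between start of trial drug administration and the last per-protocol contact will be considered on treatment".

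**The concern.** The collapsing rule and the phase table work on the same time axis but take no account of each other. A subject may have a complaint that ends shortly before a dose and returns shortly after it. The eCRF then holds two occurrences with onsets in two phases. Collapsing leaves one AE with one onset, and if that is the first onset, the phase after the dose loses the occurrence.

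Separating BI, Rifa and BI+Rifa is the purpose of the phase table, and a return of symptoms soon after dosing is something a treatment-emergent analysis should show. Protocol 1.2.2 lists nausea, vomiting and abdominal pain among the common reactions to rifampicin, so similar complaints on both sides of the period 2 BI 894416 dose are conceivable. What is at stake is the attribution of a few events in descriptive safety tables.

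**Working it through.** The plan gives no figure to reproduce on this point. The check applies the two SAP 7.8.1 conditions and onset-based phase assignment to illustrative pairs of occurrences.

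**Inputs.** The dose is at minute 0. All listed attributes are taken to match. Occurrences merge if they overlap or if gap = second start − first end ≤ 60 min. The phase is pre-dose if onset < 0 and post-dose otherwise. Two assumptions are not stated in the SAP: the collapsed AE keeps the earliest onset, and collapsing comes before phase assignment.

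| First (min) | Second (min) | Gap (min) | As written | With a stop at the dose |
|---|---|---|---|---|
| −40 to −20 | +15 to +60 | 15 − (−20) = 35 | one AE, onset −40, pre-dose | two AEs, one in each phase |
| −40 to −1 | +59 to +90 | 59 − (−1) = 60 | one AE, onset −40, pre-dose | two AEs, one in each phase |
| −40 to −20 | +45 to +60 | 45 − (−20) = 65 | two AEs | two AEs |
| −40 to +300 | +120 to +200 | overlap | one AE, onset −40, pre-dose | two AEs, one in each phase |

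If the first occurrence ended before the dose, the latest post-dose start that still merges is −1 + 60 = 59 min on a whole-minute grid. Adjacency therefore matters only in the first hour after a dose. Overlapping occurrences have no such limit, as the last row shows.

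**Effect at each boundary.** The pre-dose occurrence already puts the subject in the earlier phase, so that phase's count does not change. The change is a loss from the later phase.

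- *BI 894416, period 1.* The merged AE lies in Screening. The subject can drop out of BI and both totals in Section 15.3, and out of the disclosure displays.
- *First rifampicin dose.* The merged AE lies in BI, and the subject can drop out of Rifa. This dose is 158 h before the second BI 894416 dose (Flow Chart), and the two BI 894416 doses are at least 10 days apart (Protocol 3.1). It therefore falls at least 240 − 158 = 82 h after the first BI 894416 dose.
- *BI 894416, period 2.* The merged AE lies in Rifa. The subject can drop out of BI+Rifa and the BI total, but stays in the overall on-treatment total.

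**Size.** SAP 7.8.1 counts subjects, not events. With the 16 planned subjects in a column, one subject is 1/16 = 6.25 percentage points; with 12 it would be 1/12 = 8.33. The change occurs only if the subject has no other AE of that term in the phase concerned.

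SAP 7.8.1 also tabulates non-serious AEs with an incidence above 5% in at least one treatment. Since 6.25% > 5%, one subject can decide whether a term appears there, but only at the period 1 boundary. At the other two, the earlier on-treatment phase already counts that subject.

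**The case against.** The strongest objection is that the matching condition removes most of the cases that matter. Relationship, intensity, therapy and outcome must all be identical. Before the period 1 dose no trial drug has been given, so a Screening event should not be judged drug-related. A post-dose recurrence judged related to BI 894416 then differs on relationship and is not merged. A worsened recurrence, or one newly needing therapy, also stays separate. This stands: in period 1 the rule affects mainly events judged unrelated. Period 2 is the more plausible case, because both occurrences can be judged related.

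A second objection is that the SAP states neither the earliest-onset step nor the order of collapsing and phase assignment. It refers to a technical analysis-dataset plan, a reviewers' guide and a display standard that are not available here and might add a condition. This also stands as a limit. But if another treatment is intended, the SAP still does not say how a collapsed AE straddling a dose gets its phase.

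A third is that treating matching episodes up to an hour apart as one continuing event is defensible, and that splitting them may credit a pre-dose complaint to the new treatment. That is a fair trade-off. However, the protocol defines treatment emergence by recorded onset, and the second occurrence has its own recorded onset after the dose.

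A reader might infer more than this, in two ways. One inference is that post-dose events vanish from the report. They do not: the listings include Screening, and collapsing is for analysis only. The other is that the period 2 shift contradicts the SAP 6.1 sentence on what counts as on treatment. It does not, because Rifa is itself an on-treatment phase. Only the period 1 case is in tension with that sentence.

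**Conclusion.** The gap is real but minor. As written, SAP 7.8.1 can place a post-dose occurrence in the phase before the dose, which does not fit the onset-based rule of Protocol 7.3.4. This rests on the collapsed AE keeping its first onset and on collapsing preceding phase assignment, and it applies only to occurrences that match on every listed attribute.

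The most an affected subject changes is 6.25 percentage points in one phase for one term, with 16 subjects in the column. Few or no subjects are expected to be affected. The safety analyses are descriptive, and the pharmacokinetic endpoints and their confidence intervals are untouched. The documents do not support a claim that the trial's safety conclusions are at risk.

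**What to change.** Add a third condition to the collapsing rule in SAP 7.8.1: occurrences are collapsed only if their onsets lie in the same study analysis phase of Table 6.1: 2. Occurrences on either side of a boundary then stay separate, and each is assigned to the phase of its own onset.

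The cost is one sentence in the SAP and one programming condition, with no new data. The downside is that an intermittent event straddling a dose is counted once in each of two phases.
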